#### **A. Functional and behavioral change hypotheses**

Hypothesis A.1.

**Sheehan Disability Scale (SDS; Sheehan, 1983; Sheehan et al., 1996).** The SDS will be our primary functional outcome measure. Respondents indicate the degree to which symptoms disrupted work/school, social life, and family life/responsibilities on an 11-point scale ranging from “Not at all” to “Extremely,” and list the number of lost and unproductive work or school days. For this study, we will have participants’ index impairment caused by *PTSD symptoms* in the last month. The SDS is widely used to track disability in clinical trials and has demonstrated very good criterion (change from treatment) validity (Sheehan & Sheehan, 2008). We will use a prorated total mean score for the dimensional ratings such that only social and family ratings will be included for veterans who were not employed or attending school.

Hypothesis A.2.

**Brief Inventory of Psychosocial Functioning (B-IPF; Marx 2013).** Overall psychosocial functioning will also be assessed with this 7-item scale indexing overall level of functioning in seven life domains: romantic relationship, relationship with children, family relationships, friendships and socializing, work, training and education, and activities of daily living. Respondents indicate the degree to which they had trouble in the last 30 days in each area on a 7-point scale ranging from “Not at all” to “Very much.” The B-IPF has demonstrated concurrent validity, and the full 80-item IPF from which it was created has strong test-retest reliability and internal consistency (Marx, 2013). This scale is regularly used in PTSD clinical team settings in the VA.

**DRRI-2 (Vogt et al., 2013).** The **Post-Deployment Social Support** subscale of the DRRI will be used to assess social support resources. This subscale has excellent psychometric properties.

Hypothesis A.3.

**The CAIR Pandemic Impact Questionnaire (C-PIQ; MacLean & Cloitre, 2020).** We will measure COVID-related stress with the C-PIQ, a 19-item scale that measures COVID-19 exposure and the psychological impact of the pandemic. The C-PIQ has good psychometric properties (Lang, 2020, adapted from MacLean & Cloitre, 2020).

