### **ANALYSES**

**Inferential analyses.** The longitudinal and clustered nature of the design produces a multilevel or nested data structure (Raudenbush & Bryk, 2002), with a likelihood of between-subject variability in treatment trajectory over time (e.g. random slopes). In this study, veterans and therapists are nested (clustered) within performance sites. The lower level (level-1) data consists of the repeated measures for each individual at each assessment. Level-1 data is nested within upper level (level-2) person-level variables (e.g., study site).

Using the most up to date statistical software such as SAS 9.4 and R/R Studio, we will explore the change trajectory of endpoints over the course of pre-treatment, during-treatment, and post-treatment time intervals. Specifically, we will use the linear mixed model regression framework to assess the differential treatment effects of endpoint symptom burden over time. We will examine observed measurement scores and specify linear mixed models that best fit the time-change trends (e.g. linear, piecewise). We will test for the presence of random variation, such as between-site cluster effects and between-subject random slopes of treatment effect. We will determine the best fit linear mixed effects model as a combination of most appropriate representation of time and empirically-evidenced random and fixed effects.

The linear mixed effects models will incorporate clinically relevant time-invariant and time-varying predictors and will use Maximum Likelihood Estimation to produce estimates that are unbiased in the presence of random missingness and dropout. They will provide an Intent-To-Treat (ITT) analysis that will incorporate all available data. Per-protocol and “completer” subset analyses will be performed under the same paradigm. Additionally, a subset of subjects whom began therapy during the COVID-19 pandemic will be identified and analyzed separately; they comprise subjects which began therapy following December 31st, 2020. The tenability of the “At-Random” missingness assumption will be assessed and a sensitivity analysis of the results will be conducted to determine robustness of the inferences.

**Aim I:** Randomized controlled trial of AD-E, comparing it to PCT:

**Hypotheses 1 and 2:** Veterans in the AD-E arm will have a steeper downward slope in SDS (primary endpoint). Identical calculations will be performed with the B-IPF and DRRI-2 Post-Deployment Social Support measure.

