**Clinical significance:** Clinical significance will be calculated by the Jacobson-Truax (1991) method (e.g., Bauer, Lambert, & Neilson, 2004). This method suggests a two-step criterion. First, a reasonable cutoff between the dysfunctional and functional populations is established. Because normative data for veterans on the SDS does not yet exist, Jacobson and Truax's (1991) suggested cutoff A, defined as the point 2 *SDs* beyond the range of the pre-therapy mean (cutoff A =  $M_{clinical} - 2 SD_{clinical}$ ) will be used. Next, a reliable change index (RC) for each participant will be calculated to ensure that changes are not due to an artifact of measurement error. The RC is computed according to the following:  $RC = (x_2 - x_1)/S_{diff}$  where  $x_1$  represents the participant's pre-treatment SDS total score,  $x_2$  represents the participant's post-treatment or follow-up total score, and  $S_{diff}$  is the standard error of difference between the two test scores.  $S_{diff}$  will be calculated from the internal consistency of the measure at each time point. An RC larger than 1.96 reflects real change. Based on the two-step criterion, individuals will be classified as recovered (passed both cutoff A and RC criteria), improved (pass RC criterion but not cutoff A), unchanged (passed neither criteria), or deteriorated (passed RC criterion but symptom scores increased) for each follow-up interval. Chi-square analyses will be used to compare proportions per arm at each follow-up.

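### The reliable-change rule as written cannot recognise improvement on the SDS, and its four classes overlap and leave a gap

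*Combined protocol and SAP*

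**What the plan says.** The paragraph on clinical significance, in the ANALYSES section of the combined protocol and SAP, applies the Jacobson-Truax method to the SDS.

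- RC = (x2 − x1)/S_diff. Here x1 "represents the participant's pre-treatment SDS total score" and x2 "represents the participant's post-treatment or follow-up total score". S_diff "will be calculated from the internal consistency of the measure at each time point".
- Threshold: "An RC larger than 1.96 reflects real change". There is no absolute value and no limb for values below −1.96.
- Cutoff A is the pre-therapy mean minus 2 SD, so the functional side is the low side.
- Classes: *recovered* passes both criteria; *improved* passes RC but not cutoff A, with no direction stated; *unchanged* passes neither; *deteriorated* passes RC with a rise in score. The proportions are compared between arms by chi-square at each follow-up.

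The Measures section, under the functional hypotheses, fixes the direction of the scale: "Respondents indicate the degree to which symptoms disrupted work/school, social life, and family life/responsibilities", rated from none to extreme. It also says: "We will use a prorated total mean score for the dimensional ratings", with work/school left out for veterans neither employed nor studying. The hypotheses in the ANALYSES section treat a downward SDS slope as benefit.

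**The concern.** The subtraction runs post minus pre on a scale where benefit is a fall, yet only large positive values count as change. Programmed as written, the rule would pass veterans who got worse and fail those who got better. The class definitions add a second problem that does not depend on the sign: they do not divide the sample into separate, complete groups, which a chi-square comparison of proportions needs. A third is that the paragraph speaks of a total score while the trial's SDS score is a prorated mean.

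At stake is the plan's only patient-level statement of clinically significant change on its primary functional measure. If these gaps stay open, someone must close them during programming, possibly after arm-level results are visible.

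**Working it through.** **1. The plan's figure.** 1.96 is the two-sided 5% normal critical value (1.95996). Applied in one direction only, as worded, it is an upper-tail cut of 2.5%.

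**2. Sign.** If x2 < x1 then (x2 − x1)/S_diff < 0, which cannot exceed 1.96 for any positive S_diff. No assumption is needed.

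For illustration, take a 0–10 mean score, SD 2.0 and reliability r (all assumed), with S_diff = SD × √(2(1 − r)):

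| r | S_diff | RC, fall 8 to 2 | RC, rise 4 to 9 |
|---|---|---|---|
| 0.7 | 1.55 | −3.87, fails | +3.23, passes |
| 0.8 | 1.26 | −4.74, fails | +3.95, passes |
| 0.9 | 0.89 | −6.71, fails | +5.59, passes |

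**3. Where each veteran lands.**

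| Change in score | Cutoff A passed? | Class as written | Class if abs(RC) > 1.96 is read in |
|---|---|---|---|
| Reliable fall | yes | none | recovered |
| Reliable fall | no | unchanged | improved |
| Reliable rise | no | improved and deteriorated | improved and deteriorated |
| Not reliable | yes | none | none |
| Not reliable | no | unchanged | unchanged |

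A reliable rise that still ends below cutoff A needs a baseline below M − 2SD − 1.96 × S_diff. That is 2 + 1.96 × √(2(1 − r)) = 2.9 to 3.5 SD below the mean for r = 0.9 to 0.7, so this row can be ignored.

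The gap is easier to reach. With |RC|, a veteran can pass cutoff A without reliable change if the baseline is below M − 2SD + 1.96 × S_diff, which is M − 0.48SD, M − 0.76SD or M − 1.12SD for r = 0.7, 0.8 or 0.9.

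**4. Size, by simulation.** From the documents: SD of change 2.1 and a mean fall of 1.2 (Sample Size section; 1.2 is there a difference between arms, used here only as a plausible fall), and the SDS entry floor of 10, taken as a sum of three items, or 3.33 on the mean. Assumed: mean fall of 2.4 as an alternative, baseline mean about 6.5, SD 1.48–1.59 after the floor, reliability 0.7–0.9. Six settings were run.

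| Quantity | As written | abs(RC) read in |
|---|---|---|
| Veterans with a fall classed recovered or improved | 0% | 30.8–60.6% |
| Reliable worsening, fits both improved and deteriorated | 1.4–10.8% | 1.4–10.8% |
| No class | 22.8–41.6% | 1.7–5.7% |

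The first row on the right is recovered plus improved with a fall: 19.06 + 11.73 = 30.79 at the lowest and 38.49 + 22.06 = 60.55 at the highest. As a consistency check in one setting (r = 0.8, mean fall 1.2, baseline SD 1.48), the unclassed share as written is 24.86%. That equals the 21.30% who would be recovered plus the 3.56% in the gap.

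**5. Which SDS score.** The entry criterion of 10 or more (Inclusionary Criteria) makes sense only as a sum, because on an 11-point item scale, taken as 0–10, a mean of 10 is the maximum on every item. The Measures section uses a prorated mean. The clinical-significance paragraph says total and does not choose.

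- Ratings of 6, 6, 6 with the work item then dropped: the sum goes from 18 to 12, the mean stays at 6. With an assumed SD of the sum of 5–6 and r = 0.7–0.9, RC on the sum is −1.29 to −2.68, which can exceed 1.96 in size.
- Ratings of 9 (work), 5, 5 with the work item then dropped: the sum goes from 19 to 10, a shift of 9. The mean goes from 19/3 = 6.33 to 10/2 = 5.00, a shift of 1.33, equivalent to 1.33 × 3 = 4 on the three-item sum. The simulated reliable-change thresholds were 1.29–2.25 points, so prorating shrinks this artefact without removing it.

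**The case against.** The strongest reply is that the paragraph shows its own intent. Its threshold sentence speaks of change without direction, and *deteriorated* is set apart from the other RC-passing classes by a rise in score, which makes sense only if RC can also be passed by a fall. A sensible programmer would use |RC| > 1.96. This stands as evidence of intent, but that rule is not written, and it cures neither the overlap nor the gap.

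Three stronger readings are tempting, and the documents do not support them.

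- *The improved group would be empty.* It would not. The definition of *improved* has no direction, so veterans who reliably worsened meet it. What is true is that nobody who gets better can enter it.
- *The rule certainly uses raw sums.* The paragraph says total score, never raw, and the Measures section itself calls its score a prorated total mean. The two places need reconciling; a sum is one possible reading.
- *A visit-specific error term is a mistake.* S_diff is the standard error of the difference between two scores, and letting reliability differ by visit is defensible. The documents give no SDs or reliabilities from which harm could be shown, and there is no case for requiring a single baseline value.

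It is also fair to say that this classification is supplementary.

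**Conclusion.** The rule is wrong as written. The sign error and the faulty classes follow from the text alone. The percentages rest on an assumed baseline distribution and reliability and show only the order of size: under the two-directional reading, about 2–6% of veterans without a class and 1–11% with two.

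The consequence is limited to the clinical-significance classification and its chi-square tests. The SDS mixed model, the other outcome models and the sample size do not use RC. A reader might infer that the responder analysis cannot work at all. It can, once its evident intent is put into words. The correction should be made before anyone sees outcomes by arm.

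**What to change.** Replace the threshold and class definitions with text to this effect:

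1. With RC as post minus pre, RC ≤ −1.96 is reliable improvement and RC ≥ +1.96 is deterioration.
2. *Recovered* is reliable improvement with the score beyond cutoff A; *improved* is reliable improvement without it; *deteriorated* is RC ≥ +1.96 whatever the cutoff.
3. Every veteran without reliable change is *unchanged*, including those below cutoff A.
4. x1, x2 and cutoff A all use the prorated SDS mean from the Measures section. Note in the text that prorating reduces, but does not remove, shifts caused by a change in work or school status.

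Each assessed veteran then has exactly one class at each follow-up, and the class counts sum to the number assessed in each arm. The cost is a few sentences, with no new data and no change to the primary analysis or the sample size.

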### *Sample Size*

Power calculations were based on a two-sided, two-sample t-test to compare the differences in mean change. Effect sizes were selected based on a trial comparing Acceptance and Commitment Therapy with PCT in veterans with mental health diagnoses, using the SDS (Lang et al., 2016), which showed a large effect size for reduction in disability ( $d \approx .60$ ), a change of 1.2 points. Lang et al.'s (2016) follow-up interval was 3 months. These correspond to 3-month changes of 1.2 points assuming a standard deviation for the change of 2.1 points as per Lang and colleagues. These power calculations inflate the variance to account for clustering of scores (sites by therapists), with an  $ICC = .02$ . To partially offset possible losses to follow-up, we will follow the Benjamini-Hochberg testing procedure, which is less conservative than the Bonferroni rule (Benjamini & Hochberg, 1995). Each hypothesis is powered to compare outcome at 3 months. Analyses up to 6-months post-treatment are exploratory. Testing five hypotheses, each with Type I error of  $1\% = 5\%/5$ , then with 93 participants per arm, a two-sample t-test, comparing the difference between the 3-month changes, has 90% power to detect an absolute difference of .50 or larger assuming an effect size of .56. To have 80% power with 93 participants per arm requires an effect size of .50.

Note: In consultation with RR&D, we recalculated the number of participants to power the original trial at .8 (vs. .9) and this resulted in a new target N of 148 (74 per arm).

**COVID-19 Aim:** We used the AD grant's power framework to estimate the N required to test our hypothesis that AD would lead to better functional changes relative to PCT in COVID-19 stressed veterans with PTSD. We used the same parameters for mean change and the SD for change in Sheehan scores from the grant and a revised differential effect size prediction of .8. We reasoned that we would expect a larger differential effect size for this sub-study because AD can not only help veterans whose existing PTSD symptoms and impairments are exacerbated by COVID-19 stressors but also because AD includes change agents that can help reduce distress and impairment associated with the day to day demands and stressors of living in the time of COVID-19 (mindfulness, loving kindness meditation, letter-writing, behavioral assignments). With these parameters, we need 74 veterans (37 per arm) to power the aim (at a power of 0.90; one-tailed).

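### The four clinical-significance classes are ordered, but the planned chi-square ignores the order; if AD-MIL shifts veterans along the scale, this costs roughly 11 to 18 points of power in a supportive analysis

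*Combined protocol and SAP*

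**What the plan says.** The clinical-significance paragraph of the ANALYSES section applies the Jacobson-Truax method to SDS scores. It uses a reliable change index ("An RC larger than 1.96 reflects real change") and a cutoff two SDs from the pre-therapy mean. From these, "individuals will be classified as recovered (passed both cutoff A and RC criteria), improved (pass RC criterion but not cutoff A), unchanged" if neither criterion is met, or "deteriorated (passed RC criterion but symptom scores increased) for each follow-up interval". The comparison of arms is a single sentence: "Chi-square analyses will be used to compare proportions per arm at each follow-up".

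The paragraph names no trend or ordinal version, effect estimate, significance level, collapsing rule or small-cell rule. It gives no expected class shares, SDS reliability or baseline SD. The primary SDS analysis is separate: a linear mixed model on the continuous score. Hypothesis A.1 is directional and expects larger reductions in disability with AD-MIL.

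**The concern.** The direction of reliable change and then the cutoff rank the classes: deteriorated < unchanged < improved < recovered. A Pearson chi-square on the 2x4 table treats them as labels. It spends 3 degrees of freedom on any difference in pattern and gives the same p-value if the columns are shuffled. A consistent shift towards better classes can therefore be missed, and a significant result does not by itself say which arm did better.

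This paragraph is the plan's only analysis of whether individual SDS change is clinically meaningful, so its test should be aimed at the question asked.

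**Working it through.** **1. The plan's own figures.** There is no stated power for this comparison, so the check starts from the sample size. The Sample Size section sets two-sided 1% per hypothesis. Power = Φ(d·√(n/2) − 2.576):

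- 93 per arm, d = .56: Φ(3.819 − 2.576) = .893 (stated 90%)
- 93 per arm, d = .50: Φ(3.410 − 2.576) = .798 (stated 80%)
- 74 per arm, d = .56: Φ(3.406 − 2.576) = .797 (stated .8; "this resulted in a new target N of 148 (74 per arm")

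These reproduce without the clustering inflation that the section describes. The numbers per arm are taken as given below.

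**2. Assumptions.** Two-sided 5% for this test, since none is stated. Losses to follow-up have no stated rate, so 74 per arm and about 20% fewer (59 or 60) are shown. Class shares are assumed.

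**3. Route A: assumed shares and a common odds ratio.** PCT shares are set at 5/55/28/12% (deteriorated to recovered). At odds ratio 2, the PCT cumulative odds of .0526, 1.5 and 7.33 are halved to .0263, .75 and 3.67. AD-MIL shares become 2.6/40.3/35.7/21.4%. The plan's effect of 1.2/2.1 = 0.57 SD corresponds roughly to exp(0.57·π/√3) = 2.8. Simulated power, Pearson chi-square (3 df) against tie-corrected Wilcoxon:

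| Per arm | Odds ratio | Chi-square | Wilcoxon | Gain (points) |
|---|---|---|---|---|
| 74 | 2 | 43–44% | 60–61% | 17–18 |
| 74 | 2.5 | 69% | 84% | 15 |
| 74 | 2.8 | 80% | 92% | 11–13 |
| 59 | 2 | 35% | 51% | 17 |
| 59 | 2.5 | 58% | 75% | 17–18 |

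**4. Route B: Jacobson-Truax classes simulated from the plan's change SD of 2.1.** Assumed: baseline SD 1.5–2.0, reliability .8–.9, PCT improvement 0.5–1.5 points.

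| Per arm | d | Chi-square | Wilcoxon | Gain (points) |
|---|---|---|---|---|
| 74 | .57 | .67–.74 | .82–.87 | 12–15 |
| 74 | .50 | .54–.62 | .70–.78 | 15–17 |
| 60 | .50–.57 | – | – | 15–18 |

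**5. Analytic cross-check.** If all the signal lies along the ordering, both tests share one noncentrality, (1.96 + z)², where z is the normal quantile of the 1-df power. Power of .60, .80 and .90 on 1 df becomes .432, .645 and .784 on 3 df: losses of 17, 16 and 12 points.

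**6. Patterns that are not a uniform shift** (74 per arm, PCT 5/60/25/10%):

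| AD-MIL shares (%) | Pattern | Chi-square | Wilcoxon |
|---|---|---|---|
| 5/45/25/25 | unchanged to recovered only | .555 | .549 |
| 5/40/45/10 | unchanged to improved only | .615 | .505 |
| 10/40/25/25 | both extremes rise | .718 | .389 |

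**7. Sparse cells.** With equal arms, the expected count is pooled share × n per arm. It falls below 5 when the share is under 5/74 = 6.8%, 5/60 = 8.3% or 5/37 = 13.5%. With 148 analysed, the chance of fewer than 10 veterans in a class is 93% at a 4% share, 79% at 5%, 41% at 7% and 7% at 10%.

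In the route A scenario at odds ratio 2, the expected count per arm is 74 × (5.0 + 2.6)/2% = 2.8 for deteriorated, but 74 × (12 + 21.4)/2% = 12.4 for recovered. Recovered was sparse in about 0–1% of simulated tables at 74 per arm. In route B and similar scenarios, sparsity exceeded 50% in 13 of 24 at 74 per arm, 16 of 24 at 60, and 23 of 24 at 37.

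Chi-square type I error over six assumed class mixes was .033–.047 at 74 per arm and .027–.047 at 37, so sparse cells make it conservative. Wilcoxon stayed at about .05.

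**The case against.** The strongest reply has four parts.

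- **Wording.** Comparing proportions could mean 2x2 tests, such as improved-or-recovered against the rest. In the route A scenario at 74 per arm, that test has 58% power at odds ratio 2 and 81% at 2.5, within about 3 points of Wilcoxon. This stands as an ambiguity: the 2x4 test is the natural reading, not the only one. The same sentence of fix settles it.
- **Non-monotone effects.** The ordinal test is weaker when the effect is not a shift, and a rise in both recovered and deteriorated is a pattern one would want to see. This stands, and it is why the percentages should be kept. A significant chi-square in that case would still not show that AD-MIL helped.
- **Direction.** The per-arm proportions show direction descriptively, and the mixed model carries the directional inference on SDS. This stands; only the omnibus p-value lacks direction.
- **Importance.** No stated power, significance level or decision hangs on this test. This also stands.

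A reader might further infer that the table will usually be too sparse for a chi-square, with both recovered and deteriorated affected, and that the test is therefore invalid. The documents give no class shares to support that. Recovered was almost never sparse at 74 per arm in the main scenario, and the simulated type I error did not exceed the nominal level.

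**Conclusion.** The planned test does not use the order that the plan itself builds into the outcome. If AD-MIL shifts veterans along the scale, the cost is roughly 11 to 18 points of power at two-sided 5% with about 60 to 74 per arm. At the design's own effect (0.57 SD) and 74 per arm it is nearer 11 to 15. These figures depend on assumed class shares, significance level and dropout, and on a roughly uniform shift. The loss disappears or reverses for the other patterns shown.

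Small expected counts are a secondary matter. They are likely in the deteriorated class if its pooled share is below about 7% at 74 per arm, and likely if the classes are also compared in the 37-per-arm COVID-19 subset. They make the test slightly conservative.

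It would be wrong to infer that the trial's main conclusion is at risk. The primary SDS analysis is a mixed model on the continuous score and does not use these classes. This is an inexpensive improvement to a supportive analysis.

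**What to change.** Replace the chi-square sentence with one pre-specified ordinal comparison of the four ordered classes at each follow-up: a Wilcoxon or Cochran-Mantel-Haenszel row-mean-score test stratified by site. Optionally add a proportional-odds model giving a common odds ratio with 95% CI. Report the four percentages per arm as description, so that a simultaneous rise in recovered and deteriorated stays visible. State the significance level. If any chi-square is kept, say which table it tests and add an exact or collapsing rule for small cells.

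The cost is one or two sentences, with the same data and the software already named. The price is lower power against non-monotone patterns and, if the odds ratio is reported, a proportional-odds assumption that the rank test does not need. The change does not deal with missing follow-up data or therapist clustering in this comparison.
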